8.4 Plasma Biomarkers and Pharmacokinetic Analysis

Biomarkers, including A β 42/40 ratio, pTau181, pTau217, GFAP, NFL and potentially TDP43, will be summarized descriptively for SAF.

Plasma concentration-time data for buntanetap will be listed and summarized descriptively (number of subjects (N), mean, geometric mean, median, SD, coefficients of variation (CV), minimum, and maximum) for the SAF.

Non-compartmental analysis of one analyte (buntanetap) in blood matrix concentrations will be performed using validated computer software Phoenix. Results will be tabulated and graphically displayed using Phoenix and appropriately interpreted by a PK Scientist. Calculations will be based on the actual sampling times recorded during the study. The following PK parameters will minimally be determined, as data permit:

- Area under the curve (AUC), including AUC_{0-10hr} and AUC_{0-inf}
- Maximum concentration (C_{max}) and time of maximum concentration (T_{max})
- Terminal half-life (t½)
- Systemic clearance (CL).

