#### 12.2 Biofluids

## 12.2.1 Plasma for Biomarkers and Pharmacokinetics

Plasma samples will be collected at the baseline visit, and during the end of trial visit for analysis of biomarkers and PK, as described in the Laboratory Manual.

Confidential Page 46 of 57

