2. Mini Mental State Examination (MMSE) Score

MMSE is a brief screening instrument used to assess cognitive function (orientation, memory, attention, ability to name objects, follow verbal/written commands, write a sentence, and copy figures). Total score ranges from 0 to 30 with a lower score indicating greater disease severity.

3. Digital Symbol Substitution Test (DSST)

In the DSST individuals are asked to record associations between different symbols and numbers within time limits. The total score is the sum of all the correctly coded numbers and higher scores indicate better performance.

Exploratory

Investigate change after buntanetap in potential biomarkers

1. Plasma biomarkers

Potential biomarkers to be measured in plasma are A β 42/40 ratio, phosphorylated tau 181 (pTau181), pTau217, Neurofilament Light (NFL), Glial fibrillary acidic protein (GFAP) and TAR DNA-binding protein 43 (TDP43).

2. Pharmacokinetics (PK) Analysis

The following PK parameters will be determined: Area under the curve (AUC), C_{max} , T_{max} , $t_{1/2}$, and CL.

ANVS-22002

5 Overall Study Design

This is a 12-week randomized, double-blind, placebo-controlled, dose-ranging, multicenter clinical trial investigating the efficacy, safety, and tolerability of three different doses of buntanetap or placebo in participants with mild to moderate AD.

Qualified participants will be randomly assigned at a 1:1:1:1 ratio to one of the four treatment arms: buntanetap 7.5 mg, buntanetap 15 mg, buntanetap 30 mg, and placebo after a screening period of up to 42 days.

ADAS-Cog 11, ADCS-CGIC, ADCS-ADL, DSST, and MMSE will be assessed by clinicians who have successfully completed the requisite certifications/trainings for each assessment. All efforts will be made to ensure participants will be assessed by the same clinician throughout the study.

320 mild to moderate AD participants will be randomized to 7.5 mg, 15 mg, 30 mg of buntanetap QD or placebo.

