- The Intent-to-Treat set (ITT) will consist of all participants who are randomized. The primary
 efficacy analyses will be based on the ITT.
- The Modified Intent-to-Treat set (mITT) will consist of all participants who are randomized, receive at least one dose of study drug, and have both a baseline and at least one postbaseline assessment value for the ADAS-Cog11 or ADCS-CGIC score after taking study drug. The mITT will be used to support the primary efficacy analyses.
- The Safety analysis set (SAF) will consist of all randomized participants who receive at least one dose of study drug. The safety analyses will be based on the SAF.

- The Per-protocol set (PPS) will consist of all participants in the mITT who complete at least 67 days treatment exposure (Last dose date - First dose date + 1 >= 67 days) without any major protocol deviations that potentially could impact the primary efficacy endpoint. The membership of this analysis set will be determined prior to database lock. The PPS will be used to support the primary and secondary endpoints as supportive analyses.
- The PK set will analyze all available data from safety participants receiving buntanetap and with at least one sampling profile allowing derivation of at least one PK parameter.

Protocol deviations leading to exclusions from PPS include but are not limited to the following:

- Non-fulfilment of all inclusion criteria
- Fulfilment of at least one exclusion criterion
- Use of certain concomitant medications (for details see section 8.3.11)

The final criteria for the PPS, regarding which protocol deviations that warrant exclusion, will be determined before breaking the blind.

Baseline presentations will be based on the SAF.

Safety presentations will be based on the SAF.

Exposure to study drug will be given for the SAF.

The ITT and mITT will be analyzed according to randomized (planned) treatment. Safety and PPS will be analyzed on actual treatment.

Plasma concentration-time data for buntanetap will be based on the SAF. PK parameters derivations and statistical analyses are described in a separate PK SAP and will be based on the PK set (see Section 8.5).

8 Statistical and Analytical Plans

8.1 **Changes to the Planned Analyses**

There have been no changes in the planned analyses in the study protocol.

8.2 **Hypothesis and Statistical Methods**

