For tests of statistical significance on efficacy variables the significance level (p-value) will be provided together with the 95 percent confidence intervals (CI) of the mean, minimum, median, first and third quartiles and maximum.

[figure not shown]
Level of Significance, Multiple Comparisons and Multiplicity 8.2.1

The primary study hypothesis is that buntanetap-treatment (pooling three treatment arms together) is superior to placebo in reducing the cognitive impairment and function impairment of AD participants, as assessed by the two co-primary endpoints: change from baseline in the ADAS-Cog11 score at 12week and ADCS-CGIC score at 12-week. The two co-primary endpoints will be tested at a two-sided significance level of 5% without multiplicity adjustment. If both test hypotheses are rejected at the 5% level, the test will continue onto secondary endpoints in a hierarchical testing order, at a two-sided significance level of 5%. If one of the two co-primary endpoints is not statistically significant, the hypothesis testing for all subsequent endpoints will be considered exploratory.

To control for study-wise type 1 error rate, a fixed-sequence hierarchical testing procedure will be applied to adjust for multiplicity arising from multiple secondary endpoints. The hierarchical testing order for the secondary endpoints are:

- 1. ADCS-ADL
- 2. MMSE score
- 3. DSST

This hierarchical testing process is presented graphically below:

The study is also designed to explore the effectiveness of three buntanetap-treatment dose level. Nominal p-values will be provided for these test hypotheses of each dose arm vs. placebo, without multiplicity adjustment.

All other exploratory endpoints are considered supportive and no adjustment for multiplicity will be applied.

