8.2.3 Summary Statistics

Data will be summarized by means of summary statistics. Summary statistics will be provided for the variables described in the following sections.

Categorical data will be presented as counts and percentages, i.e., n (xx.x%). Percentages will be based on the number of subjects in the analysis data set used and given as integers. Zero frequencies will be given without percentages.

For continuous variables, these statistics will include the number of subjects, mean, SD, median, minimum, and maximum.

All variables will be analyzed descriptively with appropriate statistical methods: categorical variables by frequency tables (absolute and relative frequencies) and continuous variables by sample statistics (i.e., number of observations, mean, SD, 95% CI of the mean, minimum, median, first and third quartiles and maximum). Minimum and maximum values will be displayed as reported.

Since the two co-primary endpoints and secondary endpoints are captured at multiple visits, the method selected to analyze the endpoints, which are treated as continuous, will be a Mixed Model for Repeated Measures (MMRM). For the co-primary endpoint ADAS-Cog11 score and secondary endpoints, MMRM will be applied with change from Baseline score as the response (dependent variable) and with Baseline value as a covariate and treatment, timepoint, treatment-by-timepoint interaction as fixed effects (independent variables). The Model for co-primary endpoint ADCS-CGIC score will include treatment, timepoint, treatment-by-timepoint interaction as the fixed effects. Estimation of parameters will be done by means of Restricted Maximum Likelihood method. The Unstructured (UN) variance-covariance structure will be initially used to explore the variance-covariance matrix across visits. If the algorithm doesn't converge, a heterogeneous Toeplitz (TOEPH) as the covariance matrix will be tried first, and then first-order autoregressive (AR(1)) to achieve convergence. The Kenward-Roger approximation will be used to estimate denominator degrees of freedom. The two-sided 95% CI of the treatment differences will be presented.

The co-primary endpoint ADAS-Cog11 score and secondary endpoints will be analyzed using the model explained above as follows:

```
<Endpoint>= intercept + Base + T + V + T*V,
```

with

Base: baseline score;

T: treatment;

V: post-baseline visit (Week 6, Week 12).

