8.2.9 Exploratory Analysis

Exploratory endpoints in this clinical trial are

- Plasma biomarkers
- · PK analysis.

Plasma Biomarkers

Potential biomarkers to be measured in plasma are A β 42/40 ratio, pTau181, pTau217, NFL, GFAP and TDP43.

PK analysis

Plasma concentration-time data for buntanetap will be listed and summarized descriptively (number of subjects (N), mean, geometric mean, median, SD, coefficients of variation (CV), minimum, and maximum) for the SAF.

Plasma buntanetap PK parameters will be calculated using a non-compartmental method. Calculations will be based on the actual sampling times recorded during the study. The following PK parameters will minimally be determined, as data permit: Area under the curve (AUC), C_{max} , T_{max} , $t_{1/2}$, and CL. A separate PK SAP will include details on PK parameters derivations and statistical analyses based on the PK set.

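### The SAP sets an objective on plasma biomarker change and schedules paired samples in all arms, but prespecifies no estimate of the difference from placebo

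*SAP*

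**What the plan says.** The exploratory objective in SAP section 4 is "Investigate change after buntanetap in potential biomarkers". Protocol 12.2.1 provides the data for it: "Plasma samples will be collected at the baseline visit, and during the end of trial visit for analysis of biomarkers and PK". The schedule of events in both documents marks biomarker sampling at those two visits, with no restriction by arm. It marks none at the early discontinuation visit.

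The analysis is a single sentence in SAP 8.4. After the Aβ42/40 ratio, it says that "pTau181, pTau217, GFAP, NFL and potentially TDP43, will be summarized descriptively for SAF". SAP 8.2.9 lists the analytes and gives no method. Protocol section 6 has no biomarker analysis and leaves the detailed analysis rules to the SAP. The separate PK SAP is described in SAP 7 and 8.2.9 as covering PK parameters.

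Three general rules also bear on the point:
- SAP 8.2.3 limits the model to the clinical scales: "For the co-primary endpoint ADAS-Cog11 score and secondary endpoints, MMRM will be applied with change from Baseline score as the response". The ADCS-CGIC is modelled separately as a score.
- The same section sets a default: "All variables will be analyzed descriptively with appropriate statistical methods". For continuous variables this includes a 95% CI of the mean.
- SAP 8.2.1 states: "All other exploratory endpoints are considered supportive and no adjustment for multiplicity will be applied".

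**The concern.** The objective is about change, and the trial is randomised, placebo-controlled and dose-ranging, with a sample before and after treatment. The plan nevertheless stops short of the quantity these data are best suited to give: how far each analyte moved on buntanetap relative to placebo, pooled and at 7.5, 15 and 30 mg.

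The gap has some substance here. The rationale in Protocol 2.0 and 4.1 is that the drug lowers several neurotoxic proteins. The earlier biomarker results in AD that the protocol cites are in CSF, at 60 mg a day or more (the DISCOVER study and the AD part of the Phase 2a study). Whether the lower doses move plasma markers in AD is therefore open.

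Without a prespecified contrast, the choice of analyte, scale, adjustment and comparison is left until after the data are seen, across as many as six analytes. An informal reading of arm-level tables can miss a real shift, or take a chance baseline imbalance for a drug effect.

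**Working it through.** **Step 1: what is and is not specified.** The documents give no SD, effect size or power for any biomarker, so there is no planned figure to reproduce. The check is of the text.

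| Item | Clinical scales | Laboratory and ECG | Biomarkers |
|---|---|---|---|
| By arm and pooled | Yes (8.2.3, 8.2.7, 8.2.8) | Yes (8.3.3, 8.3.6) | Not stated |
| By visit | Yes | Yes | Not stated |
| Change from baseline | Yes, except the ADCS-CGIC, itself a rating of change | Yes | Not stated |
| Difference from placebo with CI | Yes | No | No |

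SAP 8.4 is thus less specific for biomarkers than the SAP's own laboratory and ECG sections, which are also descriptive.

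**Step 2: what a contrast with placebo would deliver.** Inputs:
- Evaluable participants: 210 pooled and 70 placebo (SAP 6). This is consistent with the planned 320, since 280/(1 − 0.125) = 320. I assume all 280 have both samples.
- Correlation r between baseline and Week 12: not given. I assume 0.6, 0.8 and 0.9.
- Equal SD at both visits. Results are in units of that SD on the analysis scale, so no SD need be assumed.

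Standard error of the difference between arms, in SD units:
- raw Week 12 means: √(1/n₁ + 1/n₂)
- change from baseline: √(2(1 − r)) × √(1/n₁ + 1/n₂)
- ANCOVA on baseline: √(1 − r²) × √(1/n₁ + 1/n₂)

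For pooled v placebo, √(1/210 + 1/70) = 0.138. For one dose v placebo, √(1/70 + 1/70) = 0.169. Multiplying by 1.96 gives 95% half-widths for raw Week 12 means of 0.271 and 0.331 SD. The other half-widths are:

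| r | Pooled, change | Pooled, ANCOVA | One dose, change | One dose, ANCOVA |
|---|---|---|---|---|
| 0.6 | 0.242 | 0.216 | 0.296 | 0.265 |
| 0.8 | 0.171 | 0.162 | 0.210 | 0.199 |
| 0.9 | 0.121 | 0.118 | 0.148 | 0.144 |

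**Step 3: gain from baseline adjustment.**
- Against raw Week 12 means the ratio of standard errors is √(1 − r²) = 0.80, 0.60, 0.44, a fall of 20%, 40%, 56%.
- Against change from baseline the ratio is √(1 − r²)/√(2(1 − r)) = √((1 + r)/2) = 0.894, 0.949, 0.975, a fall of 11%, 5%, 3%.

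**Step 4: amount of output.** Six analytes × four contrasts (pooled and three doses) = 24 intervals, or 5 × 4 = 20 if TDP43 is not assayed.

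**The case against.** The best defence is that descriptive reporting is a legitimate choice for an exploratory endpoint. The objective does not mention placebo. The analytes are described as potential ones, Protocol 4.3 is equally tentative, and SAP 8.2.1 treats exploratory endpoints as supportive. No decision in the trial depends on them. This stands, and it limits how much weight the point can carry.

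Three stronger readings are tempting, and the documents do not support them.

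- A reader might infer that the baseline samples and the placebo arm go unused. The SAF holds every randomised participant who was dosed, placebo included. The samples are paired, and the default in SAP 8.2.3 provides single-arm intervals. A table that meets SAP 8.4 could show all of this. What is missing is a prespecified difference from placebo and its interval.
- A reader might infer that the plan gives up 20% to 56% in precision. That compares ANCOVA with raw Week 12 means, a contrast the SAP does not plan. For an objective about change, the fair comparator is the change score, where the gain is 11% or less over the assumed correlations.
- A reader might infer that these markers are the trial's test of mechanism. Protocol 2.0 gives the purpose as confirming efficacy, and the panel includes NFL and GFAP, which the protocol ties to axonal integrity and inflammation.

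There is also a fair objection to modelling. Participants who stop before nine weeks attend the early discontinuation visit, where no biomarker sample is scheduled. Those who stop later are scheduled for the end of trial visit, where one is. An analysis of participants with both samples therefore selects partly on retention, with 12.5% dropout expected. This calls for disclosure, but it applies equally to a descriptive table of change.

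**Conclusion.** The point holds as a gap in the exploratory analysis. The SAP states an objective on biomarker change and collects the data to address it against placebo, but it prespecifies no such estimate, and its one sentence does not fix arm, visit or change. Primary, secondary and safety conclusions do not depend on it.

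The consequence is that, followed as written, the trial yields no planned estimate of the pharmacodynamic effect relative to placebo, either pooled or by dose. With baseline adjustment, the pooled contrast would have a 95% half-width of about 0.12 to 0.22 SD and each dose about 0.14 to 0.27 SD. These figures rest on assumed correlations of 0.6 to 0.9, equal SDs at the two visits, and complete pairs in 280 participants; fewer pairs would widen them. The efficiency gain over change scores is small. The case rests on having a prespecified, placebo-controlled estimate. The change is worth making, but it is not critical to the trial.

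**What to change.** Amend SAP 8.2.9 and 8.4 as follows.

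- Keep the descriptive tables. State that they are by arm, for the pooled buntanetap group and by visit, with change from baseline.
- For each analyte, fit an ANCOVA of log Week 12 value on randomised arm and log baseline value. Report the geometric mean ratio to placebo with 95% CI for the pooled arms and for each dose, labelled exploratory with no multiplicity adjustment.
- State that the model uses participants with both samples, explain why (no biomarker sample at the early discontinuation visit), and report the number missing by arm.
- State how values below the limit of quantification are handled before logs are taken. The SAP's only such rule is in 8.3.3, for safety laboratory values.

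The amendment should be dated before unblinding. If that point has passed, the model should be reported as post hoc.

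The cost is one paragraph and one model per analyte, with no new visits, samples or assays. The downsides are up to 24 unadjusted intervals, some of which may exclude a ratio of 1 by chance, and a completer-type subset in place of the full SAF for the modelled results.

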# 3.2. Summary of Clinical Findings

Three Phase 1 studies and two Phase 2a study have been conducted with buntanetap. For the three Phase 1 studies, the first was a single ascending dose (SAD) study in healthy volunteers; the second was a multiple ascending dose (MAD) study in healthy volunteers, and the third one was a pharmacokinetic (PK)/pharmacodynamic study of CSF in mild cognitively impaired participants (Protocol QR12001). One Phase1/2 study (Discover) was to test the safety,

Confidential Page 18 of 57

tolerability, PK and PD of buntanetap in subjects with early Alzheimer's disease (Protocol QR12005). The other Phase 2a study was a double study for both early AD and early PD participants to test buntanetap's safety, pharmacokinetics, biomarkers, and efficacy (Protocol ANVS-12003).

In the SAD trial, buntanetap was administered orally in doses of 10, 20, 40, 80, and 160 mg. Limiting side effects observed following the 160 mg dose resulted in curtailment of the study without administration of the 320 mg dose. The 160 mg dose was associated with an increased incidence of nausea and vomiting (four participants were nauseous and three vomited). Adverse events were either mild or moderate; none were severe. Buntanetap 80 mg was determined as the no observed adverse effect level.

Following oral administration, peak concentration was achieved rapidly, with mean observed  $T_{max}$  between 1.3 and 1.6 hours for both males and females at all doses.  $C_{max}$  increased with increasing dose, as did the various measures of AUC. Differences in mean observed  $C_{max}$  and AUC between males and females at each dose appeared to be related to body weight rather than gender differences.

In the MAD trial, buntanetap was administered orally in doses of 20, 40, and 60 mg 4 times a day (QID). The first two treatments were dosed for 7 days, and the third, for 10 days. Single doses were given on the first and last day to determine the pharmacokinetics of the drug. In general, the drug was well tolerated, resulting in no serious or severe adverse events and only one premature discontinuation, a participant in the 60 mg group discharged because of nausea, vomiting, dizziness and "feeling warm." The incidence of adverse events, all either mild or moderate severity, also occurred with similar frequency in the placebo group. The most common AEs were dizziness, headache, and nausea/vomiting.

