Buntanetap was absorbed rapidly after oral administration, achieving maximum plasma and CSF concentration ( $C_{max}$ ) within 1.2-1.5 hours. For the 40 and 60 mg doses, with fully defined plasma profiles, the mean terminal  $t_{1/2}$ 's were  $3.80\pm0.88$  and  $5.23\pm1.24$  hours, respectively after a single dose and  $3.53\pm1.03$  and  $4.104\pm0.91$  hours, respectively, after repeat dosing. The half-life ( $t_{1/2}$ ) of the plasma concentrations at the lower doses could not be calculated accurately. The  $C_{max}$  increased with dose (24, 144, and 2310 ng.h/mL after a single dose of 20, 40, and 60 mg, respectively and 110, 134, and 2101 ng.h/mL after multiple doses of 20, 40, and 60 mg, respectively).

In the proof of mechanism of action study (Protocol QR12001), the PK of buntanetap was measured after 10 days of administration (4x60 mg) over 12 hours in CSF and plasma of the MCI participants. The pharmacodynamics of a number of biomarkers was compared for 12 hours before the first dose at day 0 and after the last dose at day 11 of buntanetap administration. We found that the plasma concentrations of buntanetap overlapped with the plasma concentrations found in the MAD study. In this study, the N1-metabolite reached about 10 to 15%, while the level of the N8-metabolite reached about 20 to 25% of the buntanetap levels measured in plasma.

Confidential Page 19 of 57

Because a substantial proportion of the adverse events observed in AD participants treated with cholinesterase inhibitors appear to reflect the cholinomimetic properties of molecules in this class, buntanetap's highest tolerated dose is determined by the levels of the N1-metabolite in blood and brain.

While the  $t_{1/2}$  of buntanetap in plasma was 4-5 hours as seen in the SAD and MAD studies, the  $t_{1/2}$  in CSF/brain was longer than 12 hours. The concentrations of buntanetap in the brain, extrapolated from blood and CSF, were 8 times higher than in plasma. 10 days of treatment with buntanetap normalized CSF levels of sAPP $\alpha$  and  $\beta$ , tau,  $\alpha$ SYN and a series of inflammatory markers. The concentration and persistence of buntanetap in the brain suggests that much lower doses of drug administered once daily could achieve the desired pharmacological effect.

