For the Phase 2a trial (Protocol ANVS-12003), there are two parts of the study. In part one, early AD participants were given 80 mg QD buntanetap or placebo for 25 days. In the second part, early PD participants were given 5 mg, 10 mg, 20 mg, 40 mg, 80mg QD buntanetap or placebo for 25 days. In all doses and in both AD and PD participants, buntanetap was safe and well tolerated. No SAE was reported.

Buntanetap was absorbed rapidly after oral administration, achieving maximum plasma and CSF concentration ( $C_{max}$ ) within 1-2 hours. For the 80 mg doses, with fully defined plasma profiles, the mean terminal  $t_{1/2}$ 's were  $2.76 \pm 2.668$  hours. The half-life ( $t_{1/2}$ ) of the plasma concentrations at the lower doses (5 & 10 mg) could not be calculated accurately. The  $C_{max}$  increased with dose (15.31, 40.19 and 112.31 ng.h/mL after a single dose of 20, 40 and 80 mg, respectively).

Consistent with Phase 1 POC study, 80mg QD buntanetap reduced AD participants' CSF levels of sAPPα, sAPPβ, total tau, phosphorylated tau (tau181), αSYN and a series of inflammatory markers (YKL-40, GFAP, sTREM2, Complement C3). Buntanetap also improved axonal integrity shown by Neurofilament light (NFL) and synaptic function shown by neurogranin (NG). Similarly, 80 mg QD buntanetap reduced PD participants' CSF levels of αSYN and a series of inflammatory markers (YKL-40, GFAP, sTREM2, Complement C3). Buntanetap also improved PD participants' axonal integrity shown by NFL and synaptic function shown by NG.

Further, buntanetap treatment improved AD participants' cognition shown by ADAS-Cog11 and WAIS coding test and improved PD participants' movement shown by MDS-UPDRS and WAIS coding test in our Phase2a studies.

Confidential Page 20 of 57

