# 6.4. PK Analysis

Plasma concentration-time data will be analyzed by non-compartmental methods using SAS version 9.4 or greater. Calculations will be based on the actual sampling times recorded during the study. Since the study is blinded, all participants' plasma will be included in the PK analysis. From the plasma concentration-time data, the following PK parameters will minimally be determined, as data permit: Area under the curve (AUC), Cmax, Tmax, t½, and CL. Dose-proportionality may be calculated on Cmax and AUC as appropriate.

Plasma concentration-time data for buntanetap will be listed and summarized descriptively (number of participants (N), mean, median, standard deviation (SD), minimum (min), and maximum (max)) and graphically presented. PK parameters will be listed and summarized descriptively (N, mean, median, SD, min, max, and 95% CI) by each dose regimen. In addition, geometric means, and between-participant coefficients of variation (CV) will be calculated.

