# 7.2 Dosage

The study drug is to be taken orally; one capsule, once a day in the morning right before food, for 12 weeks at home. Participants are encouraged to take at least 80% of all doses (across the 12 weeks). Bottles will be examined in clinic at each clinical visit to assess compliance.

Confidential Page 32 of 57

The study drug (buntanetap capsules and placebo capsules) is manufactured under cGMP, in a manner to preserve the blind, i.e., identical color and shape orange opaque HPMC hard capsule shells and packaged 50 capsules per bottle.

Ver. 3.1; 09-25-2023

The investigational drug supply will be shipped directly to the clinical sites to dispense to participants.

Sites should order IP only after successful confirmation of all eligibility criteria (including lab results) during screening period and well ahead of baseline visit.

The dosing schedule and storage requirements will be clearly explained to the participants and study partner before dispensing the study drug.

All packaging and labelling as well as the production of study medication will be in accordance with cGMP regulations.

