#### 9.2 Baseline Visit

Sites should remind participants 1-3 days prior to their onsite visit through a telephone call. Baseline procedures include functional, cognitive, and behavioral assessments, safety assessments and a review of concurrent medications and potential adverse events that might occur. To avoid the learning effect, MMSE should be done at least three weeks after the participant's last MMSE test. The visit will consist of the following: admission procedures, including genetic material collection (blood for ApoE genotype), PK Sampling / administration of first dose, and finally, discharge procedures.

Fasting state is required for safety laboratory tests, however, cognitive, and functional assessments should not be administered when the participant is in a fasted state.

All baseline assessments should be performed on the same day. Details as below.

Confidential Page 40 of 57

Participants should arrive fasted in the morning after an overnight fast. Clinical safety labs will be drawn and sent to the central lab for analysis.

After safety lab, participants will be provided low-fat light meal before completing functional and cognitive evaluations, a physical and neurological exam, collecting vital signs, ECG, and reviewing and recording adverse events and concurrent medications. Sites should take detailed notes of the contents of all meals provided to the participants. Following completion of all these procedures, participants who continue to meet all protocol inclusion criteria and no exclusion criteria should be randomized.

If no medical or compliance concerns are identified, the participant will move on to the PK sampling phase, which will entail the following procedures:

- 1) Collect initial samples of blood (hour 0) (12ml) with venipuncture unless PI deems inappropriate with 2ml in a tube for ApoE genotype\* and 10ml in a separate tube for PK.
- 2) Administer first dose of assigned study drug after the hour 0 sampling.
- 3) Collect blood (10mL) at the 1hr, 2hrs and 4hrs timepoints. Blood should be taken within ± 10 mins of times.
- 4) Perform the final safety monitoring.

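### Sampling that ends 4 h after an oral dose cannot reliably support NCA half-life, AUC0-10hr, AUC0-inf or clearance, and the clearance obtainable is CL/F, not systemic CL

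*SAP*

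**What the plan says.** **Parameters.** SAP 8.4 plans NCA of buntanetap in Phoenix. It names AUC (both 0-10 h and 0 to infinity), Cmax, Tmax, terminal half-life and an item that begins "Systemic clearance (CL". They are a minimum set, to be derived where the data allow. SAP 8.2.9 repeats the list more briefly and leaves derivation details to a separate PK SAP, which is not among the documents. SAP 7 admits to the PK set any participant on buntanetap with a profile that yields at least one parameter.

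Protocol 6.4 plans the same type of analysis: "Plasma concentration-time data will be analyzed by non-compartmental methods using SAS version 9.4 or greater". It allows an optional dose-proportionality assessment on Cmax and AUC, without saying which AUC.

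**Sampling.** Protocol 9.2 takes a pre-dose sample at baseline and then says "Collect blood (10mL) at the 1hr, 2hrs and 4hrs timepoints". Protocol 9.4.1 repeats this schedule at Week 12. No later sample is planned at either visit.

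**Route.** Protocol 7.2: "The study drug is to be taken orally; one capsule, once a day in the morning right before food". The documents describe no intravenous data and give no bioavailability F.

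**Earlier PK (Protocol 3.2).**
- Mean Tmax in the single-dose study was "between 1.3 and 1.6 hours for both males and females at all doses". Phase 2a gives 1-2 h.
- The half-life "in plasma was 4-5 hours as seen in the SAD and MAD studies". The multiple-dose means are 3.80 and 5.23 h after a single dose and 3.53 and 4.104 h after repeat dosing, at 40 and 60 mg.
- In Phase 2a the 80 mg half-life was 2.76 ± 2.668 h, while the half-life "of the plasma concentrations at the lower doses (5 & 10 mg) could not be calculated accurately". The doses here are 7.5, 15 and 30 mg.

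**The concern.** Half-life and AUC0-inf both need a terminal slope, and clearance as dose/AUC0-inf needs it too. AUC0-10hr needs concentrations, observed or extrapolated, for 6 h after the last sample. With a peak at 1-2 h and a last sample at 4 h, little of the declining phase is observed, and it rests on one or two points. A line through two points has no residual degrees of freedom, so its fit cannot be checked.

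The clearance label is a separate matter. After an oral dose, dose/AUC estimates CL/F. Without F it cannot be turned into systemic clearance, however dense the sampling.

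At stake is the quality of the exploratory PK report. Four named parameters could appear with values set mainly by extrapolation and assay error. Both AUCs that SAP 8.4 names run past the last sample, and the interval actually observed, AUC0-4, is not named. A dose-proportionality result on either named AUC would mix any dose effect with extrapolation error. A clearance reported as systemic would be too high by the factor 1/F.

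**Working it through.** The documents give no numeric target for the PK analysis, so there is no stated figure to reproduce. The check asks how much of each parameter the schedule can observe.

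**Step 1. Count the post-peak samples.** Post-dose samples are at 1, 2 and 4 h. If the peak is at 1 h, or between 1 and 2 h, two samples follow it (2 h and 4 h). If the peak is at 2 h, one follows (4 h).

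**Step 2. Model (an assumption).** One-compartment oral model, single dose, unit scale:

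C(t) = ka/(ka − ke) × [exp(−ke·t) − exp(−ka·t)], with ke = ln 2 / t½ and ka solved from Tmax = ln(ka/ke)/(ka − ke).

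Inputs from Protocol 3.2: t½ = 2.76, 3.53, 4.1 and 5.23 h; Tmax = 1, 1.3, 1.6 and 2 h. These half-lives come from 40-80 mg doses.

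**Step 3. Area beyond the last sample.**

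AUC(0-T) = ka/(ka − ke) × [(1 − exp(−ke·T))/ke − (1 − exp(−ka·T))/ka], and AUC0-inf = 1/ke.

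Example with t½ 4.1 h and Tmax 1.3 h: ke = 0.169 and ka = 2.11 per hour; AUC0-4 = 2.645, AUC0-10 = 4.729, AUC0-inf = 5.915.
- Share of AUC0-inf beyond 4 h: 1 − 2.645/5.915 = 55%.
- Share of AUC0-10hr beyond 4 h: 1 − 2.645/4.729 = 44%.

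**Step 4. Half-life from the 2 h and 4 h samples, without error.** The estimate is 2·ln 2 / ln(C2/C4). In the example ln(C2/C4) = 0.318, giving 1.386/0.318 = 4.36 h against a true 4.1 h. The 2 h gap spans 2/5.23 = 0.38 to 2/2.76 = 0.72 of a half-life.

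**Step 5. Add measurement error.** With log-scale error of SD σ on each sample, the probability of no decline from 2 to 4 h is Φ(−ln(C2/C4)/(σ√2)). The documents give no σ, so 10%-20% is assumed. In the example at 15%: Φ(−0.318/0.212) = 6.7%.

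Results over t½ 2.76-5.23 h:

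| Tmax | AUC0-inf beyond 4 h | AUC0-10hr beyond 4 h | Error-free bias in 2-point t½ | No decline from 2 to 4 h, 10%-20% error |
|---|---|---|---|---|
| 1 h | 41%-61% | 35%-46% | +1% to +2% | 0%-18% |
| 1.3 h | 43%-62% | 37%-48% | +5% to +11% | 0%-19% |
| 1.6 h | 46%-64% | 39%-49% | +17% to +33% | 0%-21% |
| 2 h | 50%-66% | 44%-51% | +61% to +101% | 4%-28% |

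In the 2 h row the 2 h sample is itself the peak, so that slope is not a post-peak slope. In the 1.6 h row the 2 h sample is the highest of the three (for t½ 4.1 h, C1 = 0.711 and C2 = 0.750), so only the 4 h sample follows the observed peak.

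**Step 6. Spread of individual estimates.** In 200,000 simulated profiles at 15% error, t½ 4.1 h and Tmax 1.3 h, the 5th to 95th percentile of the estimates that decline is 2.1-23 h. At 10% error it is 2.5-13.9 h, and at 20% it is 1.7-26 h.

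**The case against.** The strongest reply is that the plan already protects itself. Parameters are derived only where the data allow, the PK set requires only one derivable parameter, and details sit in a PK SAP that may hold acceptance rules for slopes and extrapolation. Much of this stands, and it rules out several stronger readings that a reader might infer.

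- *The plan demands these values for every participant.* It does not. Neither the SAP nor the protocol says so, and the wording on available data points the other way.
- *The parameters cannot be obtained at all.* Too absolute. With a peak near 1 h a two-point slope is computable and nearly unbiased, though very imprecise. A minimum of three post-peak points is a convention that neither document states.
- *Half-life will be overstated by 60% or more.* That occurs only at Tmax 2 h, where the slope runs through the peak.
- *Earlier low-dose half-lives could not be calculated.* Protocol 3.2 says only that they could not be calculated accurately.
- *Dose-proportionality will rest on AUC0-inf.* Protocol 6.4 makes the assessment optional and names no AUC interval.

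The Week 12 pre-dose sample could stand in for a 24 h point at steady state. The model puts that concentration at only about 0.3%-6% of Cmax, and the documents plan no such use.

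What the reply cannot do is add a sample after 4 h. A condition on available data deals with missed samples, not with a schedule that gives no participant a later one. Nor does it correct the clearance label.

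**Conclusion.** The point holds in this form: terminal half-life, AUC0-10hr, AUC0-inf and clearance cannot be reliably estimated by NCA from samples ending at 4 h, and any clearance obtained would be CL/F. Roughly a third to a half of AUC0-10hr (35%-51%) and 41%-66% of AUC0-inf would be extrapolated. For a peak at 1-1.6 h, about 0%-21% of participants would show no decline from 2 to 4 h, rising to 28% at a 2 h peak.

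The sample count and the clearance label follow directly from the documents. The percentages rest on a one-compartment model, on half-lives from doses above those studied here, and on an assumed 10%-20% error per sample.

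A reader might infer that the trial's main results are affected. They are not: PK is an exploratory endpoint, and no efficacy or safety conclusion depends on these parameters.

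**What to change.** In SAP 8.4, the matching list in SAP 8.2.9, and the PK SAP:

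1. Make Cmax, Tmax, AUC0-4 and the Week 12 pre-dose concentration the NCA parameters.
2. Remove AUC0-10hr, AUC0-inf, terminal half-life and clearance from the NCA list.
3. Base any dose-proportionality assessment under Protocol 6.4 on Cmax and AUC0-4.
4. Label any clearance that is reported as CL/F.

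The cost is wording. No new samples or data are needed. The loss is that four named exploratory parameters are no longer reported by NCA. If half-life or clearance is still wanted, a population PK model is an option, but the correction does not depend on it.
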